18.1.2 Secondary estimand analyses

Population: Table: ITT
Listing: ITT

Statistics: The mean change in FEV1 values from baseline to Day 28 and Day 85 will be summarized using descriptive statistics (mean, median, SD, minimum, maximum, and number with missing values).

Only scheduled spirometry observations will be used for the analysis and unscheduled spirometry observations will be presented in data listing.

The MMRM model will be used for analysis of the change in FEV1 values from baseline to Day 28 and Day 85. Least-square means, standard error, 95% CI derived from the analysis model will be displayed by day for two models within the MMRM output. The first model will include change from baseline in FEV1 values as response variable, FEV1 values at baseline and day as covariates and an interaction between FEV1 values at baseline and day. Day will be specified as the repeated effect, and with SUBJECT option to account for the repeated measures within subjects. OM will be used in lsmeans statement. An unstructured covariance structure will be used to model the within-participant variability. If this analysis fails to converge, the following covariance structures will be tested in order:

1. Toeplitz with heterogeneity
2. Autoregressive with heterogeneity, by day
3. Compound symmetry with heterogeneous variances, by day
4. Toeplitz
5. Autoregressive
6. Compound symmetry without heterogeneous variances, by day

The first covariance structure that converges will be used. The Kenward-Roger approximation will be used to estimate denominator degrees of freedom. Significance tests will be based on least-squares mean using Type III sum of squares.

The second model will use absolute FEV1 values as response variable, whilst all other components remain the same as described above.

Through FEV1 data collected up to the time of treatment discontinuation will be used in the analysis. This estimates effect under the hypothetical scenario that participants do not discontinue treatment. Through FEV1 collected after treatment discontinuation will be set to missing. Missing data will be assumed to be missing at random (MAR).

A supplementary estimand will be estimated using treatment policy strategy for the intercurrent event of treatment discontinuation unrelated to the COVID-19 pandemic and using hypothetical strategy for the intercurrent event of treatment discontinuation related to the COVID-19 pandemic.

19. Other assessments

The following assessments will only be presented in data listings for the ITT population:

- Chest X-ray
- Urine Pregnancy test
- Inclusion/Exclusion criteria
- ECG
- COPD assessment test
- COVID-19 test
- Exacerbation assessment

20. Revision history

Version	Date	Change
1.0	06-Jun-2023	Initial Version
2.0	18-Aug-2023	Listings' population has been changed ENRL to ITT for section 10.2, 11.2, 12.2, 13.2, 14.2, 15.2, 16.2, 18.1.2 and 19.
3.0	29-Feb-2024	As per updated eCRF and sponsor requirement, drug compliance summary analysis added in section 11. In section 18.1.2. clarify about the unscheduled visit observations for spirometry test.
4.0	25-Apr-2024	Updated section 18.1.2 to provide clarification on inputs to the MMRM model.

21. Appendix 1: Programming Conventions for Tables, Data Listings and Figures (TLFs)

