9. STATISTICAL CONSIDERATIONS

9.1. Statistical Hypotheses

There will be no formal hypothesis testing.

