9.2. Sample Size Determination

The primary objective of the study is to evaluate the safety profile of FF/UMEC/VI over 12 weeks of treatment. The primary endpoint is incidence of AEs, SAEs and AESIs.

Sample size is determined based on the calculation of the probability of observing an AE. **Table 5** provides the probabilities of observing various numbers of AEs based on a series of theoretical risks of an event occurring in a given patient in a study of 12 weeks duration, given a sample size of 220. For example, for a theoretical risk of an AE of 1/100 in this 12 week study, we would have a greater than 89% chance of observing at least one subject having the AE.

Table 5 Probabilities of observing a given number of subjects experiencing an adverse events or more (k) for given theoretical risks in a study of 12 weeks duration for a sample size of 220 patients

k	Theoretical Risk of an Event*					
	0.0500	0.0300	0.0100	0.0050	0.0010	0.0001
1	>0.9999	0.9988	0.8904	0.6680	0.1976	0.0218
2	0.9998	0.9904	0.6469	0.3011	0.0209	0.0002
3	0.9990	0.9621	0.3776	0.0991	0.0015	<0.0001
4	0.9958	0.8984	0.1799	0.0254	<0.0001	
5	0.9866	0.7915	0.0715	0.0053		
6	0.9658	0.6488	0.0242	0.0009		
7	0.9266	0.4906	0.0071	0.0001		
8	0.8634	0.3410	0.0018	<0.0001		
9	0.7748	0.2178	0.0004			
10	0.6651	0.1281	<0.0001			

*Theoretical risk of an event occurring in a given subject in a study of 12 weeks duration.

A study with 220 evaluable participants will also provide a precision of 32ml in estimating the treatment effect of change from baseline in trough FEV1 on Day 85. The precision is defined as the half width of 95% confidence interval (CI). The calculations assume an estimate of residual standard deviation (SD) of 240mL (based on mixed model repeated measures [MMRM] analyses of Trelegy Phase IIb FULFIL study).

Total 229 participants will be enrolled in study treatment phase to achieve 220 evaluable participants at the end of the study assuming 4% withdrawal from the study treatment.

Assuming 25% screen failure rate, approximately 306 participants will be screened. If a future COVID-19 pandemic increases the number of participants that discontinue study

intervention or increases the amount of missing spirometry data the sample size may be increased. Please see [Appendix 4](#) for further details. Analysis Sets

For purposes of analysis, the following populations are defined:

Population	Description

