9.3.1. Efficacy Analysis

All efficacy analyses will be performed on the ITT Population.

The efficacy endpoints are change from baseline in trough FEV1 on Day 85, and Day 28.

The estimands for these endpoints are defined below:

- Endpoint:
 - change from baseline in trough FEV1 on Day 85 (trough FEV1 on Day 85 is defined as the mean of the FEV1 values obtained 24 hours after morning dosing on Day 84)
 - change from baseline in trough FEV1 on Day 28 (trough FEV1 on Day 28 is defined as the mean of the FEV1 values obtained prior to dosing on Day 28)
- Summary measure:
 - mean change from baseline in trough FEV1 on Day 85
 - mean change from baseline in trough FEV1 on Day 28
- Population of interest: COPD patients in India.
- Key intercurrent events: discontinuation of treatment
- Strategy for intercurrent events: a hypothetical strategy will be used for intercurrent event of treatment discontinuation. Trough FEV1 data collected up to the time of

treatment discontinuation will be used in the analysis. This estimates effect under the hypothetical scenario that participants do not discontinue treatment.

- Participants that test positive for COVID-19 will immediately discontinue study treatment. Therefore COVID-19 will be included as the intercurrent event of study treatment discontinuation and will be handled with hypothetical strategy for the estimand.

The endpoint of change from baseline in trough FEV1 will be analysed using a mixed model repeated measures (MMRM) analysis. The analysis will include change from baseline in trough FEV1 at Day 28, and Day 85. Mean change from baseline in trough FEV1 will be summarised and presented with 95% confidence interval by visit. Trough FEV1 collected after treatment discontinuation will be set to missing. Missing data will be assumed to be missing at random (MAR).

Taking prohibited medication during the treatment period is an important protocol deviation (PD) and will be included in the PD summary. However, this is not considered as an intercurrent event for the estimands.

A supplementary estimand will be estimated using treatment policy strategy for the intercurrent event of treatment discontinuation unrelated to the COVID-19 pandemic and using hypothetical strategy for the intercurrent event of treatment discontinuation related to the COVID-19 pandemic. This supplementary treatment effect will only be estimated if >5% of the ITT subjects discontinued study treatment.

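### The 95% CI for mean FEV1 change treats the observed mean baseline as fixed, so it is too narrow for the population mean whenever change depends on baseline

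*SAP*

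**What the plan says.** Protocol 9.3.1 sets the summary measure as "mean change from baseline in trough FEV1 on Day 85", with a matching one for Day 28. The population of interest is COPD patients in India.

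SAP 18.1.2 fits an MMRM to change from baseline with "FEV1 values at baseline and day as covariates and an interaction between FEV1 values at baseline and day". LS means, standard errors and 95% CIs are reported by day, using the OM option, unstructured covariance and Kenward-Roger degrees of freedom. A second model keeps the same terms but uses absolute FEV1 as the response. The section also plans descriptive statistics of the raw change, including its mean and SD, without a CI.

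Protocol 9.2 says: "A study with 220 evaluable participants will also provide a precision of 32ml". It defines that term: "The precision is defined as the half width of 95% confidence interval (CI". The SD behind it is "an estimate of residual standard deviation (SD) of 240mL (based on mixed model repeated measures [MMRM] analyses of Trelegy Phase IIb FULFIL study". Protocol 9.1 states: "There will be no formal hypothesis testing".

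Neither document says that the variability of the baseline mean is added to the LS-mean standard error. Neither gives the SD of baseline FEV1, the SD of change, the slope of change on baseline, or the covariates of the earlier study's MMRM.

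**The concern.** Baseline adjustment pays off in a randomised comparison because it removes baseline noise from the difference between arms. Here there is one arm and the target is a mean, not a contrast. With complete data, the LS mean at the sample mean baseline is simply the raw mean change. Adjustment leaves the estimate where it was and only shrinks the reported standard error.

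That smaller standard error answers a narrower question: how variable the mean change would be if every repeat of the trial enrolled patients with the same mean baseline. The stated estimand concerns COPD patients in India, from whom another sample would have a different mean baseline. If change depends on baseline, that difference carries into the mean change. Some dependence is to be expected, because baseline is a noisy measurement that is also subtracted to form the outcome.

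At stake is the coverage of the FEV1 intervals, which carry the uncertainty statement for the secondary objective.

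**Working it through.** **Inputs from the documents.** n = 220 evaluable; residual SD 240 mL; two-sided 95% interval (Protocol 9.2).

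**Inputs assumed.** SD of baseline FEV1 (SD_base) 400–500 mL; slope b of change on baseline −0.1 to −0.3. Neither is in the documents.

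**1. The plan's own figure.** Half-width = 1.96 × 240 / √220 = 31.7 mL (31.9 mL with the t quantile). The stated 32 mL reproduces.

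**2. What the model reports and what the estimand needs.** With complete data:

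- model variance of the LS mean = SD_res² / n
- sampling variance of the mean change = (SD_res² + b² × SD_base²) / n

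The model leaves out b² × SD_base² / n. OM affects how the LS mean is weighted and Kenward-Roger adjusts for estimating the covariance; neither adds this term. Because b is squared, the omission shortens the interval whatever the sign of b.

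**3. Size under the assumptions.** Coverage of the nominal 95% interval = 2Φ(1.96 × SD_res / SD_change) − 1.

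| SD_base | b | SD of change | Half-width needed | Coverage of model CI |
|---|---|---|---|---|
| any | 0 | 240 | 31.7 mL | 95.0% |
| 400 | −0.1 | √(240² + 40²) = 243 | 32.2 mL | 94.7% |
| 400 | −0.2 | √(240² + 80²) = 253 | 33.4 mL | 93.7% |
| 500 | −0.2 | √(240² + 100²) = 260 | 34.4 mL | 93.0% |
| 500 | −0.3 | √(240² + 150²) = 283 | 37.4 mL | 90.4% |

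**4. Simulation, complete data** (20,000 trials per slope, n = 220, SD_base 450 mL). The model half-width stayed near 31.8–31.9 mL at every slope. Its coverage was 95.2% at b = 0, 94.7% at −0.1, 93.3% at −0.2 and 91.4% at −0.3. An interval from the raw SD of change held about 95% throughout, with half-widths of 31.8, 32.4, 34.0 and 36.6 mL.

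**5. Simulation, two visits with dropout** (4,000 trials, 229 enrolled, 4% missing Day 85 at random, SD_base 450 mL, within-patient residual correlation 0.6 assumed). At b = −0.2 the model half-width was 31.5 mL, while the estimate's actual spread gave 33.8 mL; coverage was 93.2%. Having repeated measures and some dropout does not remove the problem.

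**6. Second model (absolute FEV1).** Since absolute FEV1 is change plus baseline, its slope on baseline is 1 + b. Slopes of −0.1 to −0.3 for change become 0.9 to 0.7. With SD_base 450 mL and slope 0.8, SD = √(240² + 360²) = 433 mL and the half-width for the population mean level is 1.96 × 433 / √220 = 57 mL, against about 32 mL reported. For slopes 0.7 and 0.9 it is 52 and 62 mL.

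**The case against.** The case on the other side is mostly about size and wording, and much of it stands.

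- **The 32 mL is not a miscalculation.** A reader might infer that it is. It reproduces, and it is the right half-width for the conditional interval the SAP plans.
- **The source of 240 mL is open.** A reader might take it as baseline-adjusted. That is plausible for an MMRM residual SD, but Protocol 9.2 lists no covariates. If it was not adjusted and is close to the SD of change, 32 mL would suit the population mean and the SAP interval would come out narrower than 32 mL.
- **The effect may be trivial.** At b = 0 there is none, and at shallow slopes it is about half a millilitre. The 90% coverage figure needs the largest assumed SD and the steepest assumed slope together. The primary objective is safety, no formal hypothesis test is planned, and there is no margin that a few millilitres could cross.
- **The raw mean and SD of change are already reported,** so a reader could form an unadjusted interval. This helps, but the printed CI remains the model's, and the raw summary lacks the model's missing-at-random handling. The two standard errors would also disagree without explanation.
- **This interval is not the trial's only inferential output.** SAP 18.1.2 has two days, two models, a supplementary estimand and a mention of significance tests.

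None of this restores the missing variance term.

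**Conclusion.** The concern holds as a minor but real mismatch between the interval and the estimand. The planned CI is conditional on the observed mean baseline and is too short for the mean change in COPD patients in India whenever b is not zero. The point estimate is not affected by this, and the safety results are untouched.

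Under the assumed inputs, the reported standard error is 1.4% to 15% too small (1 − 240/243.3 to 1 − 240/283.0). The result rests on those assumed values of b and SD_base and on 240 mL being the residual SD after baseline adjustment. The shortfall is larger for the absolute-FEV1 model if its interval is read as one for a population mean. The documents do not support saying that the interval under-covers by a known amount, or that the protocol's precision figure is wrong.

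**What to change.** Either of two changes to SAP 18.1.2 would do:

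1. Report the CI from a longitudinal model with baseline, Day 28 and Day 85 FEV1 as repeated responses, unstructured covariance and no baseline covariate, contrasting each day with baseline. This keeps the missing-at-random handling. The same model gives the mean FEV1 at each day, so it also covers the second model.
2. Keep both MMRMs and add the baseline-sampling variance to each LS-mean standard error: SE² + b² × SD_base² / n, using the estimated slope for that day and the sample baseline SD.

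Record the change in SAP section 4. Option 1 needs this in particular, because Protocol 9.3.1 describes the MMRM as modelling change at Day 28 and Day 85.

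In Protocol 9.2, state that 32 mL is the half-width given a residual SD of 240 mL, and whether that SD was baseline-adjusted; if it was, say that the figure is conditional on baseline. Alternatively, restate the precision with an SD of change, which the sponsor would have to supply.

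The cost is a slightly wider CI and small edits to the SAP and protocol text. No data collection or sample size changes.

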5.1. Inclusion Criteria

Participants eligible for enrolment in the study must meet all of the following criteria:

1. **Informed Consent:** A signed and dated written informed consent prior to study participation.
2. **Type of participant:** Outpatient.
3. **Age:** Participants 40 years of age or older at Screening (Visit 1).
4. **Gender:** Male or female participants.

Female participants:

A female participant is eligible to participate if she is not pregnant, not breastfeeding, and at least one of the following conditions applies:

- Not a woman of childbearing potential (WOCBP)

OR

- A WOCBP who agrees to follow the contraceptive guidance in [Appendix 2](#) during the treatment period and until the safety follow-up contact after the last dose of study intervention.

5. **COPD Diagnosis:** An established clinical history of COPD in accordance with the definition by the American Thoracic Society/European Respiratory Society [[Celli, 2004](#)].
6. **Smoking History:** Current or former cigarette smokers with a history of cigarette smoking of ≥ 10 pack-years at Screening (Visit 1) [number of pack years = (number of cigarettes per day / 20) x number of years smoked (e.g., 20 cigarettes per day for 10 years, or 10 cigarettes per day for 20 years)]. Previous smokers are defined as those who have stopped smoking for at least 6 months prior to Visit 1. *Note: Pipe and/or cigar use cannot be used to calculate pack-year history.*
7. Patient with history of ≥ 2 moderate exacerbations or one severe (hospitalized) exacerbation in the previous 12 months, and with a score of ≥ 10 on the CAT eligible for the study treatment in the opinion of the investigator and documented post salbutamol FEV1/FVC ratio of <0.70
8. **Existing COPD maintenance treatment:** Participant must be receiving daily long-acting maintenance treatment for their COPD for at least 3 months prior to Screening. To be eligible for the study treatment phase, participants must be compliant with their

existing COPD maintenance therapy (in the opinion of the investigator) for the preceding two weeks prior to screening.

Note: Participants receiving only short-acting COPD medications are not eligible.

9. A negative test for **active COVID-19** at Visit 1. The test should be done using a molecular (PCR or antigen test) approved by the country regulatory authorities.

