8.2.2. COPD exacerbations

For this study, a COPD exacerbation is defined as a worsening of COPD symptoms requiring the use of any treatment other than study medication or rescue salbutamol. This includes the use of antibiotics, systemic corticosteroids and/or emergency treatment of hospitalisation.

COPD exacerbation data will be collected from the start of the treatment period (Visit 2) until the safety follow up contact.

Participants will complete a paper Medical Problems worksheet to record medical problems experienced during the study. This paper worksheet must be reviewed by the Investigator (or designee) at each visit to the study site to assist in the identification of new COPD exacerbations.

All COPD exacerbations will be recorded on the COPD exacerbations page of the eCRF.

A moderate COPD exacerbation is defined as requiring systemic corticosteroids and/or antibiotics. A severe COPD exacerbation is defined as requiring hospitalization.

Every effort should be made to conduct a chest x-ray within 48 hours of identification of a moderate or severe exacerbation.

Subjects who experience a moderate or severe COPD exacerbation within two weeks prior to screening (in the opinion of the investigator) will be discontinued from the study and are not allowed to be re-screened.

COPD exacerbations are associated with the disease under study and will not be recorded as AEs unless the exacerbation meets the definition of a “serious” AE as defined in Section 10.6 of this protocol. Exacerbations that meet the definition of “serious” will be recorded on the appropriate eCRF section and should be reported to GSK, Health Authority and the Ethics Committee within 24 hours of occurrence.

Medications used to treat a COPD exacerbation will be recorded in the COPD concomitant medication section of the eCRF.

Further details on COPD Exacerbation Identification, Categorization and Treatment Guidelines are provided in [Appendix 5](#).

Note: Pulse oximetry should be measured at any time a moderate or severe exacerbation is reported or is suspected and recorded in the source documents and on the COPD exacerbation page of the eCRF if applicable.

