8.3.8. Disease-Related Events and/or Disease-Related Outcomes Not Qualifying as SAEs

COPD exacerbations are an expected disease-related outcome. COPD exacerbations should not be recorded as an adverse event, unless they meet the definition of an SAE (see Section [8.2.2](#) and [Appendix 5](#) for further details).

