10.5.2. COPD Exacerbation Severity

Each COPD exacerbation will be categorized based on severity as follows:

Mild: Worsening symptoms of COPD that are self-managed by the participant. Mild exacerbations are not associated with the use of corticosteroids or antibiotics.

Moderate: Worsening symptoms of COPD that require treatment with oral/systemic corticosteroids and/or antibiotics.

Severe: Worsening symptoms of COPD that require treatment with in-patient hospitalization.

Every effort should be made to conduct a chest x-ray within 48 hours of identification of a moderate or severe exacerbation.

Details of an exacerbation should be recorded in the exacerbation page of the eCRF. However, exacerbations should not be recorded in the AE section of the eCRF unless they meet the definition of an SAE. (Pneumonia must be recorded in the AE or SAE section of the eCRF and on the Pneumonia page of the eCRF.)

Use of antibiotics for the treatment of upper or lower respiratory tract infections will not be considered a COPD exacerbation unless the participant experiences worsening symptoms of COPD which match the definition of an exacerbation as given above.

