10.6.2. Definition of SAE

An SAE is defined as any serious adverse event that, at any dose:

a. Results in death

b. Is life-threatening

The term 'life-threatening' in the definition of 'serious' refers to an event in which the participant was at risk of death at the time of the event. It does not refer to an event, which hypothetically might have caused death, if it were more severe.

c. Requires inpatient hospitalization or prolongation of existing hospitalization

- In general, hospitalization signifies that the participant has been admitted (usually involving at least an overnight stay) at the hospital or emergency ward for observation and/or treatment that would not have been appropriate in the physician's office or outpatient setting. Complications that occur during hospitalization are AE. If a complication prolongs hospitalization or fulfills any other serious criteria, the event is serious. When in doubt as to whether "hospitalization" occurred or was necessary, the AE should be considered serious.
- Hospitalization for elective treatment of a pre-existing condition that did not worsen from baseline is not considered an AE.

d. Results in persistent or significant disability/incapacity

- The term disability means a substantial disruption of a person's ability to conduct normal life functions.
- This definition is not intended to include experiences of relatively minor medical significance such as uncomplicated headache, nausea, vomiting,

An SAE is defined as any serious adverse event that, at any dose:
diarrhea, influenza, and accidental trauma (e.g. sprained ankle) which may interfere with or prevent everyday life functions but do not constitute a substantial disruption.
e. Is a congenital anomaly/birth defect
f. Other situations:

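### Non-serious (mainly moderate) COPD exacerbations are collected as a safety assessment but appear in no summary table, so the 12-week safety profile gives no incidence for them

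*SAP*

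**What the plan says.** Protocol 8.2.2 sits under Safety Assessments. It has exacerbations recorded on their own eCRF page from Visit 2 until the safety follow-up contact. Three places keep the non-serious ones out of the AE record:

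- Protocol 8.2.2, where the definition meant is that of an SAE: "COPD exacerbations are associated with the disease under study and will not be recorded as AEs unless the exacerbation meets the definition".
- Protocol 8.3.8: "COPD exacerbations should not be recorded as an adverse event, unless they meet the definition of an SAE".
- Protocol 10.5.2: "exacerbations should not be recorded in the AE section of the eCRF unless they meet the definition of an SAE".

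Severity is defined by treatment: "A moderate COPD exacerbation is defined as requiring systemic corticosteroids and/or antibiotics", and "A severe COPD exacerbation is defined as requiring hospitalization". SAE criterion c in Protocol 10.6.2 reads "Requires inpatient hospitalization or prolongation of existing hospitalization".

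SAP section 19 introduces its list with "The following assessments will only be presented in data listings for the ITT population". The last item in that list is the exacerbation assessment.

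Inclusion criterion 7 (Protocol 5.1) requires at least two moderate exacerbations or "one severe (hospitalized) exacerbation in the previous 12 months". Protocol 4.1 has participants stop all existing COPD medications at the start of treatment, when FF/UMEC/VI begins. Rescue salbutamol continues.

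**The concern.** Each rule makes sense alone. A disease-related event can reasonably be kept off the AE page, and a secondary assessment can reasonably be listed only. Together they mean that a moderate exacerbation which meets no seriousness criterion is collected, dated and graded, yet enters no summary.

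The study's main purpose is to describe safety over 12 weeks in Indian patients with COPD. Its entry criteria select people who have recently exacerbated, and all of them change maintenance therapy on Day 1. A reader of the report will want to know how many had an exacerbation treated with steroids or antibiotics. The planned tables cannot say, and a line listing supplies neither numerator nor interval.

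**Working it through.** **1. Where each kind of exacerbation is reported**

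| Event | AE/SAE tables (SAP 14, 17) | Own summary | Listing (SAP 19) |
|---|---|---|---|
| Severe (hospitalised) | Yes, through SAE criterion c | None | Yes |
| Moderate, meeting another SAE criterion | Yes | None | Yes |
| Moderate, non-serious | No | None | Yes |

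I looked for an exacerbation count, percentage or rate in Protocol 8.2, 9.3.1 and 9.3.2 and in SAP 14 and 17, and found none. Exacerbations are not an efficacy endpoint either (Protocol 9.3.1, SAP 18).

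**2. Whether other outputs fill the gap**

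- Pneumonia must be reported as an AE (Protocol 8.2.3), and pneumonia and LRTI are AESI groups (Protocol 8.3.4). Protocol 10.5.1 classifies LRTI separately from exacerbation.
- Concomitant medications are tabulated by ATC and PT (SAP 13). Steroid and antibiotic use will show there, but Protocol 10.5.5 says antibiotics for a respiratory infection are not an exacerbation unless COPD symptoms worsen.

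These are indirect signals. None yields an exacerbation incidence.

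**3. The plan's own figure**

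Protocol Table 5 gives the chance of seeing at least one participant with an event of risk 0.01 among 220: 1 − 0.99^220 = 0.8904, as stated. Nothing in this point disputes Table 5. Its highest tabulated risk is 0.05.

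**4. Illustrative size**

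The documents give no on-treatment rate of moderate exacerbations, so the rate r is an assumption.

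- Inputs: 229 enrolled (Protocol 9.2), which is the planned ITT size if all are dosed; 84 treatment days; r from 0.25 to 2 per participant-year. The top value is the moderate-event count in inclusion criterion 7 carried forward unchanged.
- Participant-years: 229 × 84/365.25 = 52.7.
- Expected events: 52.7 × r.
- Proportion with at least one event (Poisson): 1 − exp(−r × 84/365.25).

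| r per year | Proportion affected | Participants of 229 | Events | Exact 95% CI at that count |
|---|---|---|---|---|
| 0.25 | 5.6% | 12.8 | 13.2 | 3.1% to 9.5% |
| 0.5 | 10.9% | 24.9 | 26.3 | 7.2% to 15.7% |
| 1 | 20.5% | 47.0 | 52.7 | 15.5% to 26.3% |
| 2 | 36.9% | 84.4 | 105.3 | 30.4% to 43.3% |

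SAP 14.2 summarises the most common AEs from 3% upward: 0.03 × 229 = 6.87, so 7 participants. Every assumed rate gives an expected count above that.

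**The case against.** The strongest reply is that the plan is consistent. Protocol 8.2.1 lists the safety endpoints, and exacerbations are not among them. The primary endpoint is AEs, SAEs and AESIs. The AE rule is the same in all three places and fits Protocol 10.6.1, which excludes expected manifestations of the disease under study unless they are more severe than expected. Protocol 9.3 promises no exacerbation summary, so the SAP drops nothing. With one arm and no hypothesis test, a table could not separate drug, switch and disease. The data are collected, and SAP 1.1 allows unplanned analyses if the CSR describes them. All of this stands. It explains why these events are not AEs, but not why they have no summary of their own.

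A reader might go further in three ways that the documents do not support:

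- *The plan leaves out a main harm of the drug.* Protocol 8.3.8 treats exacerbations as a disease-related outcome, the risk table in 2.3.1 does not list them as a product risk, and Protocol 2.2 reports reductions of 15% and 25% against the dual comparators.
- *Every exacerbation managed without hospitalisation is lost.* One that meets another SAE criterion is tabulated, and all are listed.
- *Participants are left without maintenance treatment.* They switch to once-daily triple therapy.

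**Conclusion.** The point holds as a reporting gap, and it should be closed. No planned summary gives the incidence of non-serious exacerbations, although the study collects them as a safety assessment and selects participants for having had them. The primary endpoint is not contradicted, and no design figure changes.

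The 6% to 37% range is an illustration, not a forecast. It assumes a constant rate, a full 84 days for all 229 despite the planned 4% withdrawal, and no variation in rate between participants. Clustering would lower the share with at least one event for the same number of events. The upper end is probably high: it carries pre-entry history unchanged into treatment, and a participant admitted on one severe event may have had no moderate ones. The conclusion does not depend on the rate, because the events go untabulated whatever their number.

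**What to change.** Take the exacerbation assessment out of the listing-only set in SAP section 19, keep the listing, and add one descriptive table on the ITT population:

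- number and percentage of participants with at least one moderate, at least one severe, and at least one moderate-or-severe exacerbation;
- number of events, and rate per participant-year with 95% CI;
- shown on treatment and again including post-treatment, to match the two safety estimands in SAP 17.1.

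State the time at risk used as the denominator for each period. Place the table apart from the AE tables and word it without attributing cause. Restricting it to moderate and severe events avoids having to settle how the self-managed mild category in Protocol 10.5.2 fits the definition in 8.2.2.

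The counting rules already exist: onset date in Protocol 10.5.6, treatment courses within 7 days merged in 10.5.4 and 10.5.5, and escalating events counted once at highest severity in 10.5.8.

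The cost is minor programming on data already collected, with no new visit, assessment or sample-size change. Severe events will appear both here and in the SAE tables, which a footnote should say.
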